3.0 Inclusion and Exclusion Criteria

3.1 Patient Inclusion Criteria:

1) 21 or older, 2) Type 2 diabetes mellitus diagnosis, 3) Seek care at family medicine or general internal medicine practices in the Chicago-land area (Northwestern) or New York City (Mt. Sinai), 4) English or Spanish speaking, 5) Take 5 or more prescription drugs for chronic conditions, 6) Adequate visual acuity and hearing, 7) Adequate cognitive capabilities to consent to participate, 8) primarily responsible for administering their own medication, 9) own a cell phone and are comfortable receiving text messages, 10) most recent hbA1c value $\geq 7.5\%$.

3.2 Provider Inclusion Criteria:

1) Resident, Attending Physician or Mid-level provider (NP, PA, pharmacist) working in General Internal Medicine, primary care, or family practice clinics within NMHC, Northwestern Medical Group, or NM Regional Medical Group (RMG) during study dates.

3.3 Adults unable to consent, individuals under the age of 21, and prisoners will be excluded from this research.

3.4 COVID-19 Survey Eligibility:

Wave 1: We will include any participant who has consented to participate in the main study and who has indicated that they were willing to be contacted for future studies run by [name] on the consent form.

Waves 2 – 4: We will include any participant who has consented to participate in the main study, who has indicated that they were willing to be contacted for future studies by [name] on the consent form, and who completed at least Wave 1 of the COVID-19 survey.

Waves 5 – 9: We will include any participant who has consented to participate in the main REMinD study, who has indicated that they were willing to be contacted for future studies by [name] on the REMinD consent form, and who completed at least Wave 1 of the COVID-19 survey.

4.0 Study-Wide Number of Subjects

- 4.1 A total of 900 patients will be enrolled in the study across all sites; about 450 from Northwestern and 450 from Mt. Sinai.
- 4.2 We expect 450 providers will be enrolled, 225 at each site.

5.0 Study-Wide Recruitment Methods

Regimen Education and Messaging in Diabetes (REMinD)

5.1 Both Mount Sinai and Northwestern will follow similar recruitment methods. The general strategy for recruitment is described here, and a more detailed description of the recruitment methods specific to Northwestern are detailed in section 22.0.

At both sites, potential participants will be identified through reports generated by the Enterprise Data Warehouse (EDW). Study staff will review the charts of identified patients to confirm eligibility that cannot be ascertained via the EDW. Among the remaining eligible patients, physician consent will be obtained to contact potential participants on their behalf. Research staff will mail patients a letter informing them of the study with the option to opt out via a toll-free number (see Recruitment Letter). Seven days after the initial mailing, a Research Coordinator will contact potential subjects by phone. Eligibility of patients will be determined from screening questions administered at this time (see Screener).

6.0 Multi-Site Research

6.1 Northwestern is the lead coordinating center for this project. Mt. Sinai is the second site of this study (Mt. Sinai Medical Center (MSMC)). Study personnel (specific names and training discussed in sections 9.4 and 20.1) will follow identical procedures to those described in the Northwestern protocol and in-person recruitment procedure in section 22.1. The Mt. Sinai approval letter is included in the IRB application.

6.2 The entire research team will meet by conference call bi-monthly before the study battery is fielded to discuss logistical issues, refinement of survey, and other issues pertaining to the study. Throughout the study Drs. [name] and [name] will conduct weekly team meetings by conference call. This time will be used to discuss progress of the study, discuss any changes that may need to be made to the protocol or study battery. The project manager will email any modifications to the IRB protocol to the Mt. Sinai PI and research coordinator within one day of receiving approval. Following approval at the Mt. Sinai site, the research coordinator will email a copy of the amendment approval letter. The Mt. Sinai PI will abide by their institution's policies. Additionally, the project manager will hold weekly meetings with project staff to ensure that the protocol is being followed.

7.0 Study Timelines

Timeline:

We are anticipating the project to be completed in 5 years. The image below describes the timeline of events for this proposed study.

Study Timeline

TASK	YEAR 1	YEAR 2	YEAR 3	YEAR 4	YEAR 5
Convene DSMB	■				
Develop, pilot test and refine assessment tools		■			
Implement, de-bug EHR tools			■		

Regimen Education and Messaging in Diabetes (REMinD)

Recruit, consent, and randomize participants											
Conduct baseline interviews											
Conduct follow-up interviews											
Seek feedback from clinic staff											
Extract EHR data											
Clean and analyze data											

Study Duration:

1. The anticipated duration of participation will be 6 months. Patients will complete an in-person or phone interview at time of consent and enrollment. They will then complete 3-month and 6-month post baseline interviews.
2. We have allotted 36 months to recruit and enroll all participants.
3. We anticipate 9 additional months to finish preliminary analysis. The estimated date to complete analysis is the end of July 2022.

8.0 Study Endpoints

8.1 The primary study endpoint will be the completion of all analyses of the Aims. A secondary study endpoint will be when all enrolled and retained participants in the trial (n=900) complete up to 6 months of follow up interviews.

9.0 Procedures Involved

9.1 We will conduct a 3-arm randomized controlled trial to test the effectiveness of UMS interventions to improve safe use and adherence to complex Rx regimens. The research at Northwestern will take place in the Primary Care, Family Medicine or General Internal Medicine clinics at Northwestern Memorial HealthCare (NMHC), Northwestern Medical Group and Northwestern Medicine Regional Medical Group. Recruitment will also be done at Mt. Sinai Medical Center (MSMC), which will be monitored by their IRB. Northwestern, as the lead site, will also be overseeing recruitment at both sites.

9.2 Intervention-related Aspects:

9.2.1 Randomization. As the UMS EHR Strategy includes changes to healthcare delivery, the intervention itself is diffuse and individual patient randomization is not feasible. Therefore, randomization will occur at the provider level (N=500 eligible clinicians; ~250 per site). This is possible with Epic; we can ‘turn on’ or off these UMS functions via physician preferences, preventing usual care physicians from having access. All consented providers will subsequently be randomized to one of the 3 study arms: **usual care**, **EHR**, or **EHR+SMS**. This process will result in a trickle down of some components of the intervention being given to patients seen by the consented provider, but not enrolled in the study for follow-up purposes (EHR tools, but not SMS). To address this, prescribers will be consented with the understanding that the care of the patients may be altered, although any risk is minimal given the educational nature of the EHR tools. This ‘turning on’ an EHR intervention with physician randomization has been previously approved by the IRB at Northwestern University for 3 other AHRQ grants [P01HS021141-01,

Regimen Education and Messaging in Diabetes (REMinD)

1U19HS021093-01 & 1R18HS017220-01]. All providers in the study will be approached prior to study initiation to provide informed consent. In all 3 studies, 100% of providers agreed to participate. To optimize the likelihood of obtaining similar populations in each study arm, physicians will be placed into four groups based on workload (full vs. part time) and health center (NMHC, NM RMG, or MSMC). [name], blinded to physician identity, will assign physicians per strata using a random number generator.

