11.0 Data and Specimen Management

11.1 Analysis Plan – Aim 1

The proposed trial uses stratified randomization with random block size to achieve group comparability and balance. Stratified by clinic, and provider type (full time, part-time, resident) randomization occurs at the provider level, where patients are randomized to the same group as their provider. Each provider (approximately 201 across the 2 sites, 100 per site) will be randomized to one of three arms resulting in approximately 67 physicians per arm. We will assume 4 patients per provider, and conservatively anticipate at least 80% retention for follow-up at six months. This will result in 900 participants recruited to the study with an anticipated minimum of 720 (240 patients per arm, 3 per physician) available after 6 months, contributing to primary data analysis.

To ensure adequate balance across treatment arms, baseline outcomes and potential confounders including socio-demographic characteristics, comorbidities, regimen complexity (i.e., # of medications, total pills taken daily), health literacy, and language will be compared across arms using descriptive statistics. Additionally, these variables will be examined one-at-a-time for associations with effectiveness outcomes, and those variables found to have significant associations with outcome(s) will be considered potential covariates in the generalized linear mixed models (GLMMs) used for formal analyses as described below. Backward stepwise model building approaches will be used to determine final, parsimonious model(s) for study outcome(s).

Prescription medication adherence at 6 months is the primary outcome of interest for Aim 1, with treatment knowledge, demonstrated proper Rx use, and regimen consolidation outcomes relevant to hypotheses of secondary interest. For each outcome, we will use generalized linear mixed-effects models (GLMMs) to test for the effects of EHR and SMS text reminders, specifying the proper link functions

Regimen Education and Messaging in Diabetes (REMinD)

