based on the distribution of the outcome variable. The GLMMs will include random provider effects and fixed binary variables for SMS text reminder and EHR to denote the intervention groups and the usual care group (H1-4). We will include a fixed indicator variable for clinic in the GLMMs and any potential confounding covariates as noted above. Analyses will be performed using PROC GLMMIX in SAS (v.9.3) and lme4 package in R. Since understanding and adherence will be assessed for each medication, 2-level GLMM will be used with medications nested in participants. We will first test for differences in the outcomes between the EHR group and usual care (H1-3), followed by comparisons between EHR+SMS vs. usual care, and EHR vs. EHR+SMS to determine additional benefits of SMS texting (H4) by constructing contrasts.

Aim 2

We will include both literacy-by-arm and language-by-arm fixed interaction terms in the above GLMMs for all outcomes. We will use the corresponding model type III tests for fixed effects to determine significance of terms, and construct appropriate contrasts for pairwise comparisons for each literacy level and each language.

Aim 3

We will determine the extent to which the interventions were implemented as planned (a process evaluation) across each site and for all three study arms, in order to optimize the intervention for future dissemination opportunities.

Mixed methods will be employed using a convergent parallel design to obtain data on intervention implementation.

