29.2 Providers being randomized to study arms
Written informed consent or online consent will be obtained from physicians (both attending and resident physicians). All participants will be told that their participation is voluntary; they can stop at any time, and whether they participated or not will not be disclosed to their superiors. Their participation in the EHR-based intervention will be kept confidential and made anonymous in reports. If the physician does not want to participate or decides to stop before completing the patient enrollment period, this will not be disclosed to any superiors.

Regimen Education and Messaging in Diabetes (REMinD)

Patients

Stratified by clinic, randomization occurs at the physician level, where patients are randomized to the same group as their physician. Therefore patients will be recruited for follow-up purposes only, rather than for consent to the EHR portion of the intervention. For patients consenting to follow-up, the consent will be documented in writing.

For those patients receiving the intervention on the basis of having a consented provider, but not approached or consented for follow-up, we request a *waiver of informed consent* because: 1) this is a low-risk study, in particular, it is research designed to evaluate an educational strategy, 2) it would not be feasible to conduct the study as intended if obtaining individual informed consent were necessary (in this case because patients do not become eligible until a prescription is written for a new or changed medicine - but a key component of the intervention is the text on the prescription), 3) informed consent from each participant would threaten the scientific validity of the study (in this case it would be impossible to evaluate real-world dissemination and implementation of the intervention if the EHR automations needed to be turned on and off at the individual patient level) and 4) for the patients receiving the intervention, but not completing follow-up, no patient data are collected that would not be routinely collected in usual care without consent.

As detailed above, this specific strategy of “turning on” an EHR intervention with physician or clinic level randomization has been previously approved by the IRB at Northwestern University for three other AHRQ funded grants (P01HS021141-01, 1U19HS021093-01 & 1R18HS017220-01).

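### Sections 9.2.1 and 11.1 give different randomisation strata, and the Aim 1 model does not force in the second stratification factor; the cost is a small loss of precision, not bias

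*Combined protocol and SAP*

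**What the plan says.** The strata appear in three places in the combined protocol and SAP.

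- **Section 9.2.1 (Randomization):** "physicians will be placed into four groups based on workload (full vs. part time) and health center (NMHC, NM RMG, or MSMC"). The person assigning arms "will assign physicians per strata using a random number generator". There is no resident level, and blocking is not mentioned.
- **Section 11.1 (Analysis Plan, Aim 1):** "The proposed trial uses stratified randomization with random block size to achieve group comparability and balance". The next sentence reads "Stratified by clinic, and provider type (full time, part-time, resident) randomization occurs at the provider level".
- **Section 29.2 (consent documentation, Patients):** "Stratified by clinic, randomization occurs at the physician level, where patients are randomized to the same group as their physician". No second factor is named.

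On the model, Section 11.1 says "The GLMMs will include random provider effects and fixed binary variables for SMS text reminder and EHR to denote the intervention groups", and then "We will include a fixed indicator variable for clinic in the GLMMs". Other covariates come from a list of patient and regimen characteristics. They are screened one at a time against the outcomes and then reduced by backward stepwise selection. Neither workload nor provider type is named in the model or in that list.

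**The concern.** Randomisation is at provider level, so the strata determine which provider characteristics are balanced across arms. Sections 9.2.1 and 11.1 differ on the second factor (two-level workload or three-level provider type), and only 11.1 treats residents as a category.

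This is more than wording. Sections 20.2 onward list 77 residents among about 117 physicians at NMHC and 140 among about 183 at MSMC. A reader cannot tell whether the arms were balanced on resident status.

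The second issue is the model. If blocked allocation balances a prognostic factor across arms and the analysis ignores it, the variance due to that factor stays in the error term although the design removed it from the arm comparison. The standard error is then too large and power is lost. Because the arm is also a provider-level variable, the random provider effect does not recover this. It carries provider-type variation into the variance of the arm contrast.

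**Working it through.** **1. The stated number of strata.** Section 9.2.1 lists 2 workloads and 3 health centers: 2 × 3 = 6. The stated four is not reproduced. It would follow from 2 workloads × 2 sites, with NMHC and NM RMG merged, but the same sentence names them separately.

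**2. Strata under Section 11.1.** Section 20.2 uses the word clinic both for a whole center and for the 14 separate RMG clinics, so there are two readings.
- Clinic means health center: 3 × 3 = 9 strata, and 201 / 9 ≈ 22 providers per stratum.
- RMG clinics counted separately, with NMHC and MSMC as one each (assumption): (1 + 14 + 1) × 3 = 48 strata, and 201 / 48 ≈ 4.2 providers per stratum for three arms.

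**3. Share of residents.** (77 + 140) / (117 + 183) = 217 / 300 = 72% of listed physicians at NMHC and MSMC. With the roughly 168 RMG physicians it is 217 / 468 = 46%. These are staffing figures, not enrolled providers.

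**4. Largest gap the plan's ICC allows.** Provider type is a provider-level factor, so its variance is part of the ICC. Section 11.2 plans for 0.001 to 0.01. With 45% adherence in usual care, total variance is 0.45 × 0.55 = 0.2475. For two equal groups a gap *d* contributes 0.25*d*². Setting 0.25*d*² ≤ 0.01 × 0.2475 gives *d* ≤ 0.0995, about 10 points.

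**5. Cost at that ceiling.** Assume provider type explains all the clustering, so that adjusting for it removes the clustering and leaves 0.99 of the variance.
- Design effect without the term: 1 + (*m* − 1) × 0.01. This is 1.020 at *m* = 3 (the plan's figure) and 1.026 at *m* = 720 / 201 = 3.58.
- Standard error ratio: √(1.020 / 0.99) = 1.015 and √(1.026 / 0.99) = 1.018.
- Power at 240 per arm, 45% vs 59%, two-sided alpha 0.0167 (sidedness is not stated): 74.3% without the term at *m* = 3 and 74.0% at *m* = 3.58, against 75.8% with it. The loss is about 1.5 to 1.8 points.
- At a 5-point gap the ICC from this factor is 0.0025. The standard error is overstated by about 0.4%, and power falls by about 0.4 points.

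The baseline of 74% to 75% is below the plan's 85% to 88%. That is a separate matter; only the differences are used here.

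**6. Simulation check.** The set-up was three provider types of near-equal size, balanced by arm, 67 providers per arm with 3 or 4 patients each, analysis of provider means, alpha 0.05 / 3 and 6,000 runs. The spreads are assumptions. The implied ICC is (2/3)*s*² / 0.2475.

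| Spread *s* | Implied ICC | Power without / with provider type | Type I error without |
|---|---|---|---|
| 0 | 0 | 73% / 73% | 1.4% |
| ±5 points | 0.007 | 73% / 74% | 1.7% |
| ±10 points | 0.027 | 71% / 75% | 1.1% |
| ±15 points | 0.061 | 68% / 77% | 1.0% |

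With the term, type I error was 1.4% to 1.9%. Only the first two rows lie within the plan's ICC range. Adding the term when it had no effect cost no visible power.

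**The case against.** The strongest defence is that the factor common to all three sections, clinic or center, is already forced into the model, that the provider random effect is there too, and that leaving out a balanced factor only makes the test conservative. All of that is correct, and it limits the point to precision and clarity. It does not close the gap: 11.1 stratifies by provider type and then does not carry it into its own model. The covariate list is open-ended, so provider type could be considered, but backward selection could then drop it.

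Four stronger readings are tempting and are not supported.

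- *Three incompatible schemes.* Section 29.2 is consent text that closely follows the 11.1 sentence without the provider-type clause. It is incomplete, not necessarily a rival scheme. The firm contradiction is between 9.2.1 and 11.1, together with the four-versus-six count inside 9.2.1.
- *Dozens of near-empty strata.* About 48 strata is one reading of clinic, and 9 is equally available. Going above 48 would mean counting NMHC pods and Mt. Sinai practice firms as clinics, which the documents do not do.
- *A large power loss.* A 20-point gap between two equal groups (say 35% vs 55%) would alone imply an ICC of 0.25 × 0.20² / 0.2475 ≈ 0.04, four times the plan's ceiling.
- *A report that cannot describe its allocation.* A report can describe the allocation performed, whatever the protocol wording. Nor does 9.2.1 say where residents fall, so one cannot claim that they were placed in a different stratum.

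The random number generator in 9.2.1 and the random blocks in 11.1 are also compatible, since one may drive the other. The text should say so.

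**Conclusion.** The point holds in limited form. Sections 9.2.1 and 11.1 describe different stratification factors, the stated four groups do not follow from the factors listed, and the Aim 1 model omits a stratification factor under either section. It would match only if randomisation was by clinic alone.

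The consequence is neither bias nor inflated type I error, but lost precision and a mildly conservative test if workload or provider type predicts adherence. Within the planned ICC range, the standard error is overstated by at most about 1.5% to 1.8% and the power loss is under about 2 points. That bound rests on two equal groups, 3 to 3.58 analysed patients per provider, a two-sided alpha of 0.0167, and provider type explaining all the clustering. The loss would be larger only if provider type pushed the ICC above 0.01. The documents give no adherence difference by provider type that would settle this.

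**What to change.** 1. State the scheme actually used in the same words in 9.2.1, 11.1 and 29.2. Give the factors and their levels, the number of strata, the blocking, whether clinic means health center, and where residents belong. Correct the count of four.
2. Enter the stratification factors actually used (center or clinic, and workload or provider type) as fixed effects in all Aim 1 mixed models, exempt from the one-at-a-time screen and backward selection.
3. If clinic strata prove sparse, use health center in the model, and say so in advance.

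The cost is protocol and SAP wording plus a few degrees of freedom: one for two-level workload or two for three-level provider type, beyond the clinic term already planned. No new patient data are needed.

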2. MedSheets. Patients will receive single-page, plain language Rx information sheets following health literacy best practices with content appropriately sequenced from a patient's perspective (drug name, indication, purpose/benefit, how to take, for how long, when to call your

Regimen Education and Messaging in Diabetes (REMinD)

doctor, when to stop taking and call your doctor, important information). These sheets pull in the UMS sig to tailor content and serve as a tangible, ‘patient-friendly’ addition to the after-visit summary.

9.7 **SMS Text Reminders.** For those patients receiving text reminders (EHR+SMS), daily text reminders will be sent for 7 days post baseline interview and following any new prescription or significant change to their regimen. The premise for the week timeframe is to help patients develop a routine for weekdays as well as weekends, when schedules may be less regimented. Continuing the SMS text reminders indefinitely runs the risk of being ignored, irritating patients, and/or adding an unwelcome expense for patients (challenging sustainability for those without unlimited texting plans). We will use an affordable, safe, premium internet SMS text service plan (EzText) to program and schedule discrete UMS-centered text messages at standard intervals for all patients based on their regimen (i.e. 1, 2, 3, or 4 times daily); patients can alter the default time points of 7:00am, 12:00pm, 5:00pm, and 10:00pm. Generic reminders are used, as the SMS text message itself is a memory support sent around the general time of the behavior. The premium plan ensures patients do not receive promotional messages with the text, and a toll-free number will be provided to patients in this study arm where they can contact us to request to cancel the service if desired, or even extend it to a daily service. An RA will orient and confirm patients can retrieve text messages, and instruct them to abstain from reading texts while driving. See Appendix for more examples of texts with common mobile phones.

9.8 **Usual Care.** For this arm, current usual care includes variable physician prescribing and/or nurse counseling, no standard distribution of Rx information or use of UMS, variable or limited distribution of Rx information in corresponding pharmacies, and no active SMS or surveillance of medication use post-visits.

9.9 **Research-related Activities:** Research related activities will include both face-to-face and telephone interviews, as well as medical chart extraction. Specific details about each research activity follow below. Data collected from face-to-face and telephone interviews will be collected using REDCap, a secure, web-based application for data collection for research studies.

Baseline Interview:

At the first interview we will ask questions about the participant’s diabetes history, and self-management behaviors related to their diabetes and medication related behaviors. We will also collect standard sociodemographic information. Participants will also complete a cognitive assessment if the interview is completed in-person. The cognitive assessment will not be completed if the baseline interview is completed over the phone.

If the baseline is completed in-person, research coordinators will also perform standardized measurements of blood pressures and pulse using an automated device (validated Omron HEM-907XL or a device with comparable accuracy). Three recordings will be performed at each visit and the mean of the second and third readings will be used to indicate the blood pressure for that visit. Patient positioning, arm selection, cuff size selection and other techniques will follow the procedures for

Regimen Education and Messaging in Diabetes (REMinD)

blood pressure measurement of the National Health Examination and Nutrition Survey. Blood pressure readings will not be performed if the baseline is completed over the phone.

During the interview the research coordinator will also look at how the participant is taking his or her medications. The research coordinator will count the number of pills within the participants' medicine bottles using a standardized protocol. Prior to beginning, the RC will put on gloves and will sanitize the automatic pill counter and counting stick. While wearing gloves, the coordinator will pour the entire bottle onto the automatic counter. The pill counter will automatically transfer the pills into the bottom compartment and will count the pills as they are transferred. Once the pills are in the bottom compartment, the coordinator will return the pills back into the bottle. The coordinator will place the cap on the bottle, making sure the cap is securely in place. For phone interviews, RCs will read a standardized script to ask patients to count study pills using a standardized procedure. If able, participants will be asked to join a video call so the RC can take a screen shot of the patient's remaining pills-per bottle. The RC will save the screen shot/photograph to the study project folder within the secure GIM server only using the patient's studyid to identify the photograph. No PHI will be captured in the photograph. If the participant does not have video capabilities, the RC will proceed to explain how the patient can count their pills and relay the number to the RC. This script is outlined in the interview script.

This interview will take place in-person in a private room in the clinical offices of the Family Medicine, Primary Care, or General Internal Medicine of NMHC, Northwestern Medicine Regional Medical Group, Northwestern Medical Group, Northwestern Medicine Grayslake, Northwestern Medicine Lake Forest, Delnor Hospital, Northwestern Medicine affiliated clinics, or in community sites in the participant's neighborhood (i.e. private study rooms in libraries). For interviews that are not able to be completed in-person, the RC will complete the interview over the phone from a closed office/private room. The interview will take about 90 minutes to complete.

Follow up Interviews (3 months, 6 months)

Participants will also be asked to participate in two follow-up interviews at 3 months and 6 months post-baseline interview.

The 3 month interview will take place over the phone and patients will be asked additional questions about how they take their medicines, their diabetes as well as gather information about receipt of UMS tools, filled prescriptions and text reminders.

The 6 month follow-up interview will take place in-person or over the phone and will gather information about receipt of UMS tools, filled prescriptions, text reminders, self-report of physician medication-related communication at recent encounter as well as complete 3 additional blood pressure readings, and the pill count. The blood pressure reading will be excluded if the interview must be completed over the phone. If the interview is completed over the phone, the same pill count protocol for baseline will be followed for 6 month. For patients consented before May 19, 2020, a brief

Regimen Education and Messaging in Diabetes (REMinD)

script will be read informing patients of the change in the consent in regards to the pill count. The RC will ask the participant to provide verbal consent to allow the study team to take a screen shot/photograph of the patient's pills during a video call in order for the RC to count the pills after the interview. The patient will be notified that no PHI will be captured in the photograph.

At the 6 month interview, in addition to the activities that will take place during the 3 month interview, patients from the intervention arm will also be asked additional, semi-structured questions to explore 1) personal challenges with regimen adherence, 2) perceived value of the EHR and SMS tools, 3) unmet needs and acceptability of other tools and approaches to support medication use.

Clinic Staff Feedback

Among consenting physicians, we will ask physicians to complete a brief survey about their experience using the tools. (See Provider feedback survey)

Medical Record Extraction:

Additional chart data will be abstracted via an additional EDW report including patient medications, chronic conditions, COVID-19 diagnosis an/or results of antibody test, and healthcare utilization (ED, hospitalization, primary care appointments) as well as hypertension, diabetes and cholesterol clinical values. Furthermore, we will extract whether patients received prescription orders in UMS format (with after-visit summaries) and the corresponding. We will also note when (days post visit) the Medication reconciliation sheet was incorporated into the EHR.

Field Notes:

The project manager will meet monthly with clinic administrators to document any changes that might have occurred and when. This will include relevant change to clinic staffing, workflow, EHR, or any significant event that could potentially alter the delivery and subsequent effectiveness of intervention. The project manager will keep a document of this.

Retention Activities:

In order to maintain high retention of enrolled participants we will mail holiday cards to participants annually. In addition, if we are unable to contact enrolled participants we will mail or email "Trying to Reach You" letters to re-engage participants. Data sources for this study will include in-person and telephone interviews with participants (see attached surveys), and medical record data extraction via the EDW.

For patients that complete COVID-19 Waves 5-9:

★ **Patient Interviews.** Participants will complete up to five telephone interviews in total, with one interview taking place every 4 months. New, supplement-specific data collection related to COVID-19 will be collected via telephone interviews; this survey is equivalent for both Aim 1 and Aim 2 activities, as data collection will be conducted in parallel.

★ **EHR data.** Medical record data will be collected via the Electronic Health Record (EHR) from January 1, 2019 - present. EHR data will confirm comorbidities

Regimen Education and Messaging in Diabetes (REMinD)

and medications. We will also extract clinical outcomes (HbA1c, diastolic and systolic blood pressure, cholesterol (LDL, HDL, total, triglycerides), GFR, COVID-19 lab tests and results, COVID-19 diagnosis, COVID-19 vaccine type and dates, and antibody results), preventive services utilization (cancer screening, immunizations), and health services use (clinic visits (including telehealth), medical subspecialty visits, emergency department visits, hospitalizations). Lastly, we will collect patient portal usage.

★ **Pharmacy fill data.** Participants will be asked if they use Walgreens or CVS to fill their prescriptions. During the consent process, participants will be informed that Walgreens and CVS Pharmacy may access, receive, or use their personal information, based on the pharmacies they utilize. *Data Collection:*

All interview measures and timepoints are listed in the table below.

Variable	Instrument(s) or Measure(s)	Source	Timing & Window		
			0	3M	6M
			60 - 120 days	5M - 8M?	
Outcome Measures			In-person or phone	Phone	In-person or phone
Medication Adherence	ASK-12	Matza, 2009	x	x	x
	24-hour recall		x	x	x
	Pill Count		x		x
Proper medication use	24-hour recall		x	x	x
Medication consolidation	24-hour recall		x	x	x
Treatment knowledge	Identification of drug purpose		x	x	
Clinical outcomes	HbA1c	chart	x		x
	systolic/diastolic blood pressure	in-person	x		x
Patient Covariates					
Medication Regimen Characteristics	Prescription medication, complexity (MRCI)	George, 2004	x		x
	drug class	George, 2004	x		x
Health status	Overall Health (Global)	PROMIS	x		x
	Comorbidities	Goodman, 2013	x		x
	Depression - SF (4 item)	PROMIS	x		

Regimen Education and Messaging in Diabetes (REMinD)

Health Literacy	NVS, Brief health literacy screener	Weiss, 2005; Chew, 2008	x		
Cognitive Status	MMSE	Folstein, 1975	x		
Patient Activation	CHAI	[name], 2017	x		x
Social Support	Tangible Support	Wolshin, 1997	x		
Sociodemographics	Age, sex, race/ethnicity, education, income, language, English proficiency, country of origin, time in US	self-report	x		
Patient Process Outcomes					
Patient/Provider Communication	CAHPS - Providers discuss medication decisions		x	x	x
Perceived Values of EHR and SMS Tools	Open-ended questions				x
Unmet needs and acceptability of tools	Open-ended questions				x
Personal challenges with medication regimen	Open-ended questions				x
System Process Outcomes					
Receipt of UMS Materials	Receipt of MedSheet (yes/no), UMS Sigs (yes/no), MedList (yes/no)	self-report, chart	x	x	x
Receipt of SMS text reminders	Receipt of SMS (yes/no)	self-report		x	x
Intervention impact on clinic practice	Provider Survey				x
Changes throughout intervention within clinic practice	Field notes with administrative staff				
Cost Outcomes					
Initial programming cost of EHR tools			x		
Programming maintenance costs for EHR					x
Running UMS technologies	Printer ink, paper, staff time		x		
SMS monthly costs			x		

9.10 COVID-19 Survey. We are proposing an optional sub-study to be conducted from a pool of existing studies conducted by [name] (LitCog (STU00026255), REMinD (STU00203777), COPD Multimorbidity (STU00201640), UMS Portal (STU00201639), and TAKE IT (STU00204465). Participants will be invited to participate

Regimen Education and Messaging in Diabetes (REMinD)

in an optional one-time brief (5-10 minute) telephone survey to capture one additional outcome pertaining to their knowledge, attitudes, and beliefs about the COVID-19 outbreak in March 2020. They will also be asked a series of patient-reported health literacy items. This new data will be linked with participant characteristics from the parent study. Participants who complete the COVID-19 survey will receive a \$10 gift card in the mail.

Recruitment will be done by phone by trained Northwestern RAs. We will contact anyone who has indicated that they were willing to be contacted for future studies run by [name] on the consent form. Verbal consent will be obtained prior to completing the one time brief (5-10 minute) telephone survey.

Waves 2-4:

From the same pool of existing studies included in Wave 1, any participants who completed the Wave 1 COVID-19 survey will be contacted and invited to participate in up to 3 additional telephone surveys (10-30 minutes each) over the course of 4 months to continue to evaluate knowledge, attitudes, and beliefs over time about the ongoing COVID-19 pandemic. Participants who complete the follow-up interviews will receive a \$10 gift card in the mail for wave 2 and a \$15 gift card for waves 3 and 4 (per survey), for a total of up to \$40 for the follow-up activities. For wave 3 and 4, we increased the participant compensation from \$10 to \$15 due to the longer survey administered at this time point.

Recruitment will be done by phone by trained Northwestern RAs. We will invite anyone who has indicated that they were willing to be contacted for future studies run by [name] on the consent form and who completed the Wave 1 survey. Verbal consent for the follow up waves will be obtained prior to completing the Wave 2 telephone survey (initiated 2 weeks after Wave 1). Participants who consent to these follow-up activities will be re-contacted for completion of Waves 3 and 4 at 1 month and 3 months post-wave 2.

Waves 5-9:

In March 2020, we recruited a subset of the REMinD cohort (n=136), and patients enrolled in four other studies (n=537; Total N=673) to form the Chicago COVID-19 Comorbidities (C3) cohort study. We initially completed four phone interviews (described above) with them to better understand how older adults with underlying health conditions, at greater risk for COVID-19 complications, were responding and taking action (or not) to prevent infection and disease spread.

We will now continue our investigation to better understand the longer-term impact of COVID-19. From the same pool of existing studies, any participants who completed the Wave 1 COVID-19 survey will be contacted and invited to participate in up to 5 additional telephone surveys occurring every 4 months. Interviews will collect information on participants' responses to COVID-19 and changes in lifestyle behaviors, healthcare utilization, physical and mental health, access and adherence to treatment, socioeconomic circumstances and clinical outcomes. We will also collect data from the medical record and pharmacy record abstractions.

Regimen Education and Messaging in Diabetes (REMinD)

Participants who complete additional telephone surveys will receive compensation in the mail. See section 22.2 for further details.

Data from all waves of the COVID-19 telephone surveys will be captured in REDCap.

this study (STU00208130) in order to create a final and complete dataset..

